8. EFFICACY MEASURES

8.1 STUDY MEASURES

Dermatologist Investigator assessed tolerability parameters: dryness, erythema, scaling, and irritation will be assessed separately for each side of the face. All assessments will be made on a 5-point ordinal scale (0=none, 1=minimal, 2=mild, 3=moderate, 4=severe) at baseline, 24 hours, week 1, and week 2.

Subject assessed tolerability parameters: dryness, tightness, stinging, itching, and burning will be assessed separately for each side of the face. All assessments will be made on a 5-point ordinal scale (0=none, 1=minimal, 2=mild, 3=moderate, 4=severe) at baseline, 24 hours, week 1, and week 2.

Noninvasive Biomeasurements: TEWL and corneometry measurements on the right and left cheek will be conducted at baseline, 24 hours, week 1, and week 2.

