12. STATISTICAL METHODS

Along with descriptive statistics (means, standard deviations and percentages), investigator and subject ordinal nonparametric results will be analyzed using Wilcoxon signed rank test and sign test for paired comparison at different time points. The noninvasive parametric results will be analyzed using paired t-test. Changes will be considered significant at the alpha level of 0.05.

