Please let us know if you are experiencing any of these problems. Please use the following scale: 0=none, 1=minimal, 2=mild, 3=moderate, 4=severe. A lower number means you do not have the problem. Circle your correct response. Please rate both your cheeks separately.

Ask the study staff if you have any questions.

RIGHT CHEEK

Visits	Baseline	24 Hours	Week 1	Week 2
Dryness	01234	01234	01234	01234
Tightness	01234	01234	01234	01234
Stinging	01234	01234	01234	01234
Itching	01234	01234	01234	01234
Burning	01234	01234	01234	01234

LEFT CHEEK

Visits	Baseline	24 Hours	Week 1	Week 2
Dryness	01234	01234	01234	01234
Tightness	01234	01234	01234	01234
Stinging	01234	01234	01234	01234
Itching	01234	01234	01234	01234
Burning	01234	01234	01234	01234

NONINVASIVE ASSESSMENTS

	Baseline	24 Hours	Week 1	Week 2
TEWL Right Cheek				
TEWL Left Cheek				
Corneometry Right Cheek				
Corneometry Left Cheek				

ADVERSE EVENT

Did the subject experience any adverse event? Yes or No *If yes, list below:

Adverse Event	1	2
Start Date mm/dd/yy		
Stop Date mm/dd/yy		
Ongoing*		
Frequency ¹		
Severity ²		
Relation to Study Med ³		
Action Taken ⁴		
Outcome ⁵		
Serious (Y/N)		
¹ Frequency ² Severity 1=Continuous 1=Mild 2=Intermittent 2=Moderate 3=Isolated 3=Severe	³ Relation to Study Med 1=Not related 2=Possible 3=Probable 4=Definite	⁴ Action Taken (insert all codes that apply) 1=None 2=Study drug discontinued 3=Non-drug therapy 4=New OTC or R _x drug added

⁵Outcome

1=Resolved

2=Improved

3=Stabilized

4=Ongoing

5=Worsened

6=Lost to follow-up

*Check only if the adverse event is ongoing when subject completes/exits the study.

**Refer to the protocol for definitions of severity and relationship to study product.

Final Subject Status				
The s	ubject completed the study. Date Completed: Month Day	Year		
The streason:	ubject discontinued the study prematurely due to the following O	DNE		
	Date Discontinued: Month Day	Year		
discontinua	Adverse event, including intercurrent illness, which required study tion (specify) Protocol violation (specify)	-		
	Lost to follow-up Subject decision/withdrawal of consent			
	Other (specify)	?		

Investigator's State	ement:
information record	pages of this case report form. To the best of my knowledge, the led on the case report form is a complete and accurate record of ment course during the study.
Signature	Printed Name
Date Signed:	nth Day Year

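### One instruction on the subject tolerability form contradicts the form's own scale, and could lead a subject with a slight symptom to circle 0

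*Combined protocol and SAP*

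**What the plan says.** Section 8.1 sets the scale for the subject ratings: "All assessments will be made on a 5-point ordinal scale (0=none, 1=minimal, 2=mild, 3=moderate, 4=severe". The subject form in Appendix I repeats it, "Please use the following scale: 0=none, 1=minimal, 2=mild, 3=moderate, 4=severe", and follows it at once with "A lower number means you do not have the problem". The form closes its instructions with "Ask the study staff if you have any questions".

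Section 8.1 lists the subject's items, "dryness, tightness, stinging, itching, and burning will be assessed separately for each side of the face", and the investigator's, "dryness, erythema, scaling, and irritation will be assessed separately for each side of the face". The investigator form in Appendix I carries the same five anchors without the extra sentence.

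Section 12 plans inference on these scores: "investigator and subject ordinal nonparametric results will be analyzed using Wilcoxon signed rank test and sign test for paired comparison at different time points". Sections 12.5.1 and 12.5.2 make corneometry the primary and TEWL the secondary endpoint.

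**The concern.** The sentence is part of the instruction that subjects read each time they rate themselves. It equates a low score with having no problem, whereas the scale gives that meaning to 0 alone. A subject who feels slight stinging and takes the sentence at its word may decide that something so slight does not count, and circle 0.

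At stake is the ability of the subject ratings to show a small difference between the treated and untreated cheek. Section 11.1 says the products rarely irritate the skin, so low scores are the likely range. The study sets out to show lack of barrier damage, so lost low-grade symptoms would make the treated side look better tolerated than it was.

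**Working it through.** No figure in the plan can be reproduced here. The check compares the two instructions and follows the result into the planned tests.

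**Step 1: the sentence against the anchors.** Inputs: the subject form in Appendix I and the matching scale in Section 8.1.

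| Score | Meaning on the scale | Literal reading of the sentence | Agree? |
|---|---|---|---|
| 0 | none | absent | yes |
| 1 | minimal, so present | low number, so absent | no |
| 2 | mild, so present | low number, so absent | no |
| 3, 4 | moderate, severe | not low numbers | no conflict |

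Sections 7.2 and 8.1 nowhere give the meaning of absence to any score but 0. The realistic risk is at 0 versus 1, since a subject is less likely to take a score labelled mild as absence.

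**Step 2: how many ratings the sentence governs.** Inputs: 5 subject items, 2 cheeks, 4 visits, 50 subjects.

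- Per subject: 5 × 2 × 4 = 40 ratings. If all 50 complete: 40 × 50 = 2,000.
- Dryness is the only item on both forms. The other 5 − 1 = 4 items are graded by the subject alone: 4 × 2 × 4 = 32 of the 40 ratings.

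These are counts of ratings exposed to the wording, not of ratings expected to be wrong.

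**Step 3: what a misreading does to a paired difference.** Write each pair as (treated, untreated), with d = treated − untreated.

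| True pair | Recorded pair | d, true to recorded | Effect |
|---|---|---|---|
| (1, 0) | (0, 0) | 1 to 0 | difference becomes a tie |
| (1, 1) | (0, 0) | 0 to 0 | none |
| (2, 1) | (2, 0) | 1 to 2 | same sign, larger size |
| (0, 0) | (1, 1) | 0 to 0 | none |

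The first row matters most, because it is the pattern a slight reaction to a product used on one side would give. A tie carries no information in the sign test, nor in the Wilcoxon signed rank test when zero differences are dropped (Section 12 does not say how they are handled). If the comparison is with baseline instead, a baseline 0 followed by a true 1 recorded as 0 is also a tie. The third row can enlarge a difference, so the effect is a tendency to hide small differences and not a rule.

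**Step 4: size.** This would need the distribution of true scores and the share of subjects who misread the form. The documents give neither. Section 12.1 says only that the sponsor chose 50 subjects, with no effect size, standard deviation or power. No estimate can be derived.

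**The case against.** The best defence is that the form largely corrects itself. Every number is labelled immediately before the disputed sentence: a subject with no symptom sees 0 marked none, and one with slight stinging sees 1 marked minimal. The sentence was probably meant only to show direction, lower being less. Ratings are made at site visits, and staff can be asked. The subject ratings are neither primary nor secondary endpoint, the side-blinded investigator also grades tolerability, and adverse events are collected separately.

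Most of this stands, and it makes the point minor. It does not make the sentence correct. Asking staff helps only a subject who notices the conflict, and apart from dryness the investigator grades none of the items that the subject grades.

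A reader might infer more than the documents support:

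- *That grading of mild irritation is compromised.* Irritation is an investigator item, and the investigator form lacks the sentence.
- *That the loss can be quantified.* Suppose a 15-point gap between cheeks in the share with any symptom, a fraction f of that gap due to slight symptoms, and a share m of those recorded as 0 equally on both cheeks. The recorded gap is 15 × (1 − f × m). With f = 0.5 and m = 0.10 it is 14.25 points; with f = 1 and m = 0.40 it is 9.0. All of these inputs are assumptions without a source in the plan, so the range measures only the assumptions.
- *That symptom-free subjects circling 1 add noise to the comparison.* A subject who does so on both cheeks contributes a difference of zero, just as with two 0s. It would alter the descriptive percentages but not the paired difference.
- *That the study's main conclusion is at risk.* The objective is judged by corneometry and TEWL, which do not depend on this form.

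**Conclusion.** The wording error is real and visible on the form: the sentence is false for scores 1 and 2. Its likely consequence is some slight symptoms recorded as 0, with ties and a tendency to miss small side-to-side differences in subject-rated tolerability. That rests on the assumption that some subjects follow the sentence over the anchors, which is plausible but not shown. The size is unknown. Severity is minor, and neither the sample size nor the analysis needs to change.

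**What to change.** Replace the sentence on the subject form with: *0 means you do not have the problem at all. 1 to 4 mean you have it, from minimal (1) to severe (4).* Do this before the first baseline visit, so that all four visits use the same instruction. Ratings already given under the present wording could not be collected again.

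The cost is one revised page. The form belongs to the protocol's Appendix I, and Section 14.4 requires written approval of revisions from both the sponsor and the IRB before they are used, so notifying the IRB is not enough.
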